Document Date: 10.01.2020

NCT: NCT03436147

Vaginal-assisted laparoscopic sacrohysteropexy (VALH) and vaginal hysterectomy+vaginal vault suspension (VH+VVS) for advanced uterine prolapse: 12month preliminary results of a randomized controlled study Materials and Methods

In this study, the first-year results of a single-center, randomized controlled study of two parallel groups, conducted in the tertiary referral training and research hospital, were evaluated. The study included women who were admitted to our urogynecology unit for stage 2–4 symptomatic uterine prolapse between June 2017 and January 2019. The study was approved by our hospital's local ethics committee (approval number: 2018/23).

Requirements for participation were that the women be over 18 years of age with no desire to preserve fertility (subjects had completed childbearing or were practicing reliable contraception), have a normal size uterus (< 10 cm) on examination or ultrasound, and agree to participate in principle. They were then given further information about the trial, and consent was sought either in an outpatient clinic or at the next visit for preoperative assessment. Exclusion criteria were: cervical elongation (surgeon's discretion), prior prolapse surgery, current foreign-body complications, increased risk or recent history of cervical dysplasia, chronic pelvic pain, significant uterine abnormalities, abnormal menstruation or postmenopausal bleeding within the previous 12 months, and a significantly enlarged fibroid uterus or concomitant medical problems precluding general anesthesia or the assumption of a steep Trendelenburg position. Written informed consent was obtained from all of the participants.

Participants were randomly assigned to either of two groups: Group A (VALH) or Group B (VH+VVS). The consolidated standard of reporting trials (CONSORT) flow study diagram is presented in Figure 1. Simple randomization was performed by the distribution of blind envelopes in order to separate the patients into the groups; this randomization was performed before admission to surgery. Those who subsequently had a strong preference for either operation and consequently declined to continue in the study were excluded and not put through the randomization process.

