The measure for the primary outcome was treatment failure, defined as recurrent apical prolapse that required surgery within the first year after initial surgery. The secondary outcome measures were changed in anatomy quantified by POP-Q and symptoms quantified using the ICIQ-VS questionnaire scores for prolapse, quality of life, and PGI-I, UDI-6, IIQ-7 scores. Other secondary outcome measures were operation time, pain score, blood loss, and postoperative hospital stay.

Statistical analysis

Data analysis was performed with SPSS (version 20.0; Chicago, IL). Data were analyzed using descriptive statistical methods (mean, standard deviation, median, frequency, rate, minimum, and maximum). One sample Kolmogorov–Smirnov test was performed to analyze the distribution of the data. For group comparisons of parameters with quantitative data showing normal distribution, Student's t-test was used, while a Mann–Whitney U test was used for comparing other parameters not showing normal distribution. A p value of less than .05 was considered statistically significant.

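### The yes/no primary outcome has no planned between-group estimate or confidence interval; a risk difference with a sparse-event interval should be added

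*Combined protocol and SAP*

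**What the plan says.** The paragraph just before the Statistical analysis section defines the endpoint: "The measure for the primary outcome was treatment failure, defined as recurrent apical prolapse that required surgery within the first year after initial surgery". That is a 0/1 outcome for each woman.

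The Statistical analysis section then contains:

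- **Description:** "Data were analyzed using descriptive statistical methods (mean, standard deviation, median, frequency, rate, minimum, and maximum". Frequency and rate can cover the number and percentage of failures in each arm.
- **Distribution check:** "One sample Kolmogorov–Smirnov test was performed to analyze the distribution of the data".
- **Group comparison:** "For group comparisons of parameters with quantitative data showing normal distribution", followed by "Student's t-test was used, while a Mann–Whitney U test was used for comparing other parameters not showing normal distribution".
- **Decision rule:** "A p value of less than .05 was considered statistically significant".

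Neither this section nor any other part of the document names a risk difference, risk ratio, odds ratio or confidence interval, or a test for categorical data.

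**The concern.** The sentence on group comparisons is built for quantitative measures such as operation time, blood loss and questionnaire scores. The primary outcome is not one of these, and the text can be taken in two ways:

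- If the parameters sent to Mann–Whitney are only the remaining quantitative ones, no between-group analysis of the primary outcome is planned.
- If they are all remaining variables, the primary analysis is a Mann–Whitney p-value on 0/1 data.

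In neither case does the plan produce an estimate of the difference in failure or a statement of its precision. That matters most when failures are few. A non-significant p-value may then be read as a sign that the two operations work equally well, although the data remain compatible with a sizeable difference. An interval would show this. It would not supply the missing information, but it would stop its absence from being hidden.

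**Working it through.** **Plan's own figure.** There is none to reproduce. The document states no sample size, arm size, expected failure rate, margin or failure count. The arm sizes, counts and rates below are therefore assumptions. Equal arms are a further simplification, because simple randomisation by envelope does not guarantee them.

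**Formulas.** With x failures among n women, p = x/n and z = 1.96 (z² = 3.8415), the Wilson limits (l, u) are

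[p + z²/(2n) ± z·√(p(1−p)/n + z²/(4n²))] / (1 + z²/n).

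The Newcombe 95% interval for d = p₁ − p₂ runs from d − √[(p₁−l₁)² + (u₂−p₂)²] to d + √[(u₁−p₁)² + (p₂−l₂)²].

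On 0/1 data the tie-corrected Mann–Whitney test without continuity correction equals the Pearson chi-square multiplied by (N−1)/N, where N is the total in both arms.

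**1. No failures in either arm.** With x = 0, l = 0 and u = z²/(n + z²), so the interval is ±u.

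| Assumed n per arm | Calculation | 95% interval, percentage points |
|---|---|---|
| 20 | 3.8415/23.8415 | ±16.1 |
| 30 | 3.8415/33.8415 | ±11.4 |
| 50 | 3.8415/53.8415 | ±7.1 |

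Mann–Whitney here gives 1.0 or no value, depending on software settings. One implementation returns 1.0 with its default continuity correction and no value without it. SPSS, which the plan names, was not checked. Either output is uninformative and would be the same at every arm size, while the interval changes by more than a factor of two.

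The chance of this outcome at 30 per arm is 0.98⁶⁰ = 29.8% if both true failure rates are 2%, and 0.95⁶⁰ = 4.6% if both are 5%.

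**2. Two failures against one, 30 per arm.**

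- First arm: p₁ = .0667, Wilson limits .0185 to .2132.
- Second arm: p₂ = .0333, Wilson limits .0059 to .1667.
- d = .0333.
- Lower limit: .0333 − √(.0482² + .1334²) = .0333 − .1418 = −.108.
- Upper limit: .0333 + √(.1466² + .0274²) = .0333 + .1491 = +.182.

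The interval is −10.8 to +18.2 points. For the test, Pearson chi-square = 60·(2·29 − 28·1)²/(30·30·3·57) = .351. Multiplied by 59/60 this is .345, giving p = .56.

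**3. What the p-value leaves out.** With 1 failure against 3, the Mann–Whitney p-value (continuity-corrected) stays at .31 to .32 for every assumed arm size from 20 to 100. The Newcombe interval goes from −31.4 to +11.0 at 20 per arm (42.4 points wide) to −7.5 to +2.9 at 100 per arm (10.4 points wide). The p-value barely moves while the precision improves about fourfold.

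**The case against.** The case against treating this as serious is substantial, and most of it stands.

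- **The test is not wrong.** A reader might infer that Mann–Whitney is invalid here or inflates false positives. It does neither: on 0/1 data it is close to a chi-square. Across 175 tables (all splits of 1 to 10 failures at 20, 30, 40, 50 and 60 per arm), it gives the same verdict at .05 as the Newcombe interval in 166. In the other nine, Mann–Whitney is significant and the interval includes zero, but its lower limit passes zero by only 0.05 to 0.64 points. The choice of test matters little.
- **Per-arm rates can be reported.** Frequency and rate are listed, and an outsider could compute the interval from failures and denominators. That is true if both are published for this outcome, which the text does not expressly promise. A rate for each arm is still not an estimate of the difference.
- **Nothing claims equivalence.** The document makes no claim of equal effectiveness or non-inferiority, and its title calls the results preliminary. The misreading is a risk, not something the plan commits.
- **The sizes are assumed.** They show how sparse binary data behave; they do not measure a defect in this trial.
- **The timing is late.** The text is written in the past tense ("In this study, the first-year results of a single-center, randomized controlled study of two parallel groups") and carries "Document Date: 10.01.2020", while admissions ran to January 2019. One-year outcomes were complete or nearly so, and a change now may be a reporting improvement rather than a prospective safeguard.

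What survives is narrower: followed as written, the plan answers its only primary question with at most a p-value.

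**Conclusion.** The gap is real and should be closed, but it is a cheap improvement and does not invalidate the trial. The plan names no between-group estimate, no interval and no clearly applicable comparison for its sole primary outcome. On assumed figures of 30 per arm, differences of up to 11.4 points in either direction remain possible after 0 against 0 failures, and −10.8 to +18.2 points after 2 against 1. Other arm sizes and counts would change these numbers, but not the conclusion that a p-value does not convey them.

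Two stronger readings go too far. The documents do not support saying that the primary analysis must fail when neither arm has a failure: the p-value is uninformative, but whether it is undefined depends on software. Nor do they show that the investigators intended to present a non-significant result as equal effectiveness.

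**What to change.** In the Statistical analysis section, limit the Kolmogorov–Smirnov, t-test and Mann–Whitney rule to quantitative measures, and add:

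> Treatment failure is reported per arm as number of failures, denominator and number with unknown one-year status. The between-group result is the risk difference (VALH minus VH+VVS) with a Newcombe 95% confidence interval. Fisher's exact p-value is supportive. A p-value of .05 or more is not taken as evidence of equal effectiveness.

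Another interval suited to sparse events, or Boschloo's test in place of Fisher's, would serve equally well if named. Date the change, and label it post hoc if outcomes by arm had already been seen. The analysis population and the counting of women with unknown status also need stating, but they are separate matters.

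**Cost.** A few sentences and no new data; the interval is closed-form from the counts and denominators. There are three drawbacks:

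- Post hoc status, if it applies, weakens the change.
- The Newcombe interval is somewhat conservative when failure is rare (exact coverage 97.3% to 100% at equal rates of 2% to 5%).
- Significance is slightly harder to reach at very small counts, as in the nine of 175 tables above.
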